8.6.2.2.2 Echocardiographic Exclusion Criteria

- 1. Left atrial appendage anatomy which cannot accommodate a commercially available control device or the CLAAS Implant per manufacturer IFU (e.g., the anatomy and sizing must be appropriate for both the investigational (CLAAS) and a commercially available device in order to be enrolled in the trial).
- 2. Intracardiac thrombus or dense spontaneous echo contrast consistent with thrombus, as visualized by TEE prior to implant.
- 3. Left ventricular ejection fraction (LVEF) <30%.
- 4. Moderate or large pericardial effusion >10mm or symptomatic pericardial effusion, signs or symptoms of acute or chronic pericarditis, or evidence of tamponade physiology.
- 5. Atrial septal defect that warrants closure.
- 6. High risk patent foramen ovale (PFO), defined as an atrial septal aneurysm (excursion >15mm or length >15mm) or large shunt (early [within 3 beats] and/or substantial passage of bubbles, e.g., ≥20).
- 7. Moderate or severe mitral valve stenosis (mitral valve area <1.5cm²).
- 8. Complex atheroma with mobile plague of the descending aorta and/or aortic arch.
- 9. Evidence of cardiac tumor.

8.7 Informed Consent

Subject participation in this clinical study is voluntary. Informed Consent is required from each subject or his/her legally authorized representative. The Investigator is responsible for ensuring that Informed Consent is obtained prior to the use of any investigational devices, study-required procedures and/or testing, or data collection.

The obtaining and documentation of Informed Consent must be in accordance with the principles of the Declaration of Helsinki, ISO 14155:2020, any applicable national regulations, and local IRB/REB/EC and/or Regulatory authority, as applicable. The ICF must be accepted by Conformal or its delegate (e.g., CRO), and approved by the site's IRB/REB/EC, or central IRB, if applicable.

Conformal will provide a study-specific template of the ICF to investigators participating in this study. The ICF template may be modified to meet the requirements of the investigative site's IRB/REB/EC. Any modification requires acceptance from Conformal prior to use of the form. The ICF must be in a language understandable to the subject and if needed, Conformal will assist the site in obtaining a written consent translation. Translated consent forms must also have IRB/REB/EC approval prior to their use. Privacy language shall be included in the body of the form or as a separate form as applicable.

Failure to obtain subject consent will be reported by Conformal to the applicable regulatory authority according to their requirements (e.g., FDA requirement is within 5 working days of learning of such an event). Any violations of the informed consent process must be reported as

deviations to the sponsor and local regulatory authorities, as appropriate. If new information becomes available that can significantly affect a subject's future health and medical care, that information shall be provided to the affected subject(s) in written form via a revised ICF or, in some situations, enrolled subjects may be requested to sign and date an addendum to the ICF. In addition to new significant information during a study, other situations may necessitate revision of the ICF, such as if there are amendments to the applicable laws, protocol, a change in Principal Investigator, administrative changes, or following annual review by the IRB/REB/EC. The new version of the ICF must be approved by the IRB/REB/EC. Acceptance by Conformal is required if changes to the revised ICF are requested by the site's IRB/REB/EC. The IRB/REB/EC will determine the subject population to be re-consented.

8.8 Study Enrollment Process and Subject Classification

Potentially eligible subjects who meet all general inclusion criteria, and no general exclusion criteria and who have consented to participate in the trial will undergo the protocol-specified screening assessments to confirm eligibility. Sites will maintain a subject screening log in the EDC to document the reasons for meeting study criteria but failing to be enrolled.

8.8.1 Roll-In Population

A Roll-In ITT subject is an individual who signs an ICF, is assigned to the Roll-In Cohort by the site and has an implant procedure attempted. For this population, an implant procedure attempt (ITT established) is defined when the LAAO Access Sheath is introduced into the body.

If an implant procedure is attempted without an implant placed, the subject must be followed through the Primary Safety and Efficacy Endpoints (at all visits including 7-days, 45-days, 6-months, 12-months, and 18-months) assessing only: QVSFS, AE Assessment, and Concomitant Medication Assessment. These assessments can be conducted via telehealth/phone call. These subjects will not be required to have subsequent protocol mandated imaging and will not be required to follow the medication requirements. If a subject in the Roll-in population experiences a suspected stroke or systemic embolism, the subject should be brought in for an Unscheduled Visit (in-person clinic visit) for assessment per the Schedule of Assessments matrix. After the 18-Month visit, these subjects will have completed all required study assessments.

Subjects who are scheduled for a roll-in procedure, but no longer meet eligibility criteria and do not have a procedure attempt (i.e., the access sheath never entered the body) will be followed only through 45 days via telehealth/phone call visits. No protocol mandated imaging or medication therapy will be required. After the 45-Day visit, these subjects will have completed all required study assessments and will be classified as Screen Failures.

8.8.2 Conscious Sedation Population

The Conscious Sedation ITT subject is an individual who signs an ICF, has been assigned to the Conscious Sedation Cohort and has an implant procedure attempted. For this population, an implant procedure attempt (ITT established) is defined when the CLAAS Delivery Catheter is introduced into the body.

If an implant procedure is attempted without an implant placed, the subject must be followed through the Primary Safety and Efficacy Endpoints (at all visits including 7-days, 45-days, 6-months, 12-months, and 18-months) assessing only: QVSFS, AE Assessment, and Concomitant Medication Assessment. These assessments can be conducted via telehealth/phone call. These subjects will not be required to have subsequent protocol mandated imaging and will not be required to follow the medication requirements. If a subject in the Conscious Sedation Population experiences a suspected stroke or systemic embolism, that subject should be

brought in for an Unscheduled Visit (in-person clinic visit) for assessment per the Schedule of the Assessments matrix. After the 18-Month visit, these subjects will have completed all required study assessments.

Subjects who are scheduled for a conscious sedation procedure, but no longer meet eligibility criteria and do not have a procedure attempt (i.e., the CLAAS Delivery Catheter never entered the body) will be followed only through 45 days via telehealth/phone call visits. No protocol mandated imaging or medication therapy will be required. After the 45-Day visit, these subjects will have completed all required study assessments and will be classified as Screen Failures.

8.8.3 Randomized Population

A Randomized subject is an individual who signs ICF and is found to meet all eligibility criteria and is randomized. When a subject is randomized, he/she will be included in the Intention to Treat population.

The Randomized Population includes two groups: 1) subjects who undergo LAAO Procedure and 2) subjects who after randomization and prior to the study procedure are found to no longer meet eligibility criteria. Examples include subjects after randomization while awaiting the procedure fall and sustain a fractured hip. Also included are subjects who are brought to the Cardiac Catheterization Laboratory who on baseline TEE evaluation are found to have thrombus in the LAA.

Subjects who are randomized, no longer meet eligibility criteria (group 2 above) must be followed through the Primary Safety and Efficacy Endpoints with telehealth/phone call visits (at all visits including 7-days, 45-days, 6-months, 12-months, and 18-months) assessing only: QVSFS, AE Assessment, and Concomitant Medication Assessment.

These subjects will not be required to have subsequent protocol mandated imaging and will not be required to follow the medication requirements. If a subject in the Randomized Population group experiences a suspected stroke or systemic embolism, that subject should be brought in for an Unscheduled Visit (in-person clinic visit) for assessment per the Schedule of Assessments matrix. After the 18-Month visit, these subjects will have completed all required study assessments.

8.8.4 Attempted Population

The Attempted Population includes all ITT subjects in whom a LAAO procedure has been attempted, i.e., the LAAO access sheath was inserted into the body.

The Attempted Population includes two groups: 1) subjects who undergo LAAO Procedure and receive a LAAO Closure Device and 2) subjects in whom a undergo the procedure without receiving a LAAO device.

Following index procedure hospitalization discharge, these subjects in the Attempted Population who do NOT receive an implant will not be required to have subsequent protocol mandated imaging and will not be required to follow the medication requirements. Subjects who do not receive an implant must be followed through the Primary Safety and Efficacy Endpoints with telehealth/phone call visits (at all visits including 7-days, 45-days, 6-months, 12-months, and 18-months) assessing only: QVSFS, AE Assessment, and Concomitant Medication Assessment. If a subject in the Attempted Population group experiences a suspected stroke or systemic embolism, that subject should be brought in for an Unscheduled Visit (in-person clinic visit) for assessment per the Schedule of Assessments matrix. After the 18-Month visit, these subjects will have completed all required study assessments.

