7.4.1.3 Delivery System

The CLAAS system is delivered to the target location at the LAA ostium using standard interventional techniques and imaging to ensure appropriate placement and sizing. Under echocardiographic guidance, a transseptal puncture is used to place an Access Sheath. A pigtail catheter may be advanced over a guidewire via the Access Sheath into the LAA to perform an angiogram of the LAA. In addition, Echocardiography is also used at the time of the procedure to guide the sizing and delivery of the implant.

Delivery of the Implant is achieved with a customized coaxial delivery system (nominal dimensions provided in Table 2). Vascular access is achieved with the Conformal Access Sheath with Dilator (nominal dimensions provided in Table 3). The Implant is loaded into the distal end of the CLAAS Delivery Catheter as outlined in the Instructions for Use. The system is designed with sufficient length to access the LAA from a femoral vein puncture. The CLAAS Delivery Catheter working length is designed such that when it is locked to the Access Sheath, its distal tip is about 3cm short of the Access Sheath tip. This allows the user to advance the Implant from the CLAAS Delivery Catheter into the Access Sheath prior to deploying it into the subject. The Delivery System includes the Access Sheath with Dilator and the CLAAS Delivery Catheter. The Delivery System components are shown in Figure 4.

The Access Sheath and Dilator systems are provided in two different sizes to accommodate the different implant sizes and are also offered as either single or double curves to accommodate varying vascular anatomy. The Single Curve Access Sheath has a single, 90-degree bend at its distal end with a radius of 3.5 inches. The Double Curve Access Sheath has a double curve, which is an anterior curve distal to the primary curve. The Access Sheath components are shown in Figure 5. The VizaraMed Multiflex Steerable Sheath 15.5F has been evaluated for compatibility with the Regular (27 mm) CLAAS System and may be used as an alternative to the Regular Conformal Access Sheath. The 15.5F VizaraMed Multiflex Steerable Sheath is not compatible with the Large (35 mm) CLAAS System.

Table 2: CLAAS Delivery Catheter Nominal Dimensions

Component	Regular	Large		
CLAAS Delivery Catheter				
Outer diameter	15.2F	17.1F		
Inner diameter	13.3F	15.3F		
Working length	73cm	73cm		

Table 3: CLAAS Access Sheath Nominal Dimensions

Component	Regular	Large
Access Sheath		

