9.5.6 Transseptal Puncture

Percutaneous femoral vein access and transseptal puncture should be performed per physician standard practice using a standard commercially available transseptal access system.\

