14.2 Analysis Populations

Section 8.8 describes the different subject classifications in the study. The ITT Randomized population will be used to analyze the Primary Safety and Efficacy Endpoints. Additional analyses of different populations (Attempted and Implanted) will be considered supportive in nature for the Primary Safety and Efficacy Endpoints and will the utilized to examine other Secondary Endpoints. Additional analyses of populations who receive the Initial CLAAS System vs. the Next Generation CLAAS System will be performed.

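### Procedures abandoned after a puncture complication but before LAAO sheath entry fall outside the Attempted and Roll-In ITT sets, and a roll-in subject may then be followed for only 45 days

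*Protocol*

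**What the plan says.** Section 8.8.4 limits the Attempted Population to ITT subjects in whom "a LAAO procedure has been attempted, i.e., the LAAO access sheath was inserted into the body". Section 8.8.1 sets the same point for the Roll-in cohort, where "an implant procedure attempt (ITT established) is defined when the LAAO Access Sheath is introduced into the body". The Appendix A entries for the Attempted and Intended populations also turn on insertion of the LAAO Access Sheath.

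The order of steps is given elsewhere. Section 9.5.6 states: "Percutaneous femoral vein access and transseptal puncture should be performed per physician standard practice using a standard commercially available transseptal access system". Section 7.4.1.3 adds that "a transseptal puncture is used to place an Access Sheath".

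Section 14.2 analyses the primary endpoints in the ITT Randomized population. For the others it says "Additional analyses of different populations (Attempted and Implanted) will be considered supportive in nature" with respect to those endpoints, and it also assigns them to the other secondary endpoints.

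For roll-in subjects who have become ineligible, section 8.8.1 provides that those who "do not have a procedure attempt (i.e., the access sheath never entered the body) will be followed only through 45 days", by telephone or telehealth, and are then classed as Screen Failures. A roll-in subject with an attempt but no implant is followed through 18 months.

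**The concern.** Two invasive steps precede the moment at which the plan says an attempt begins. Section 12.7.1 links the procedural risks to transseptal puncture and lists perforation, tamponade and venous access complications among them. Perforation, drained effusion and major vascular complications are also components of the primary safety endpoint (section 8.5.1). If such an event stops the case before the LAAO sheath is placed, the event itself takes the subject out of the Attempted set. Membership of a set meant to describe procedural safety then depends on a safety outcome.

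The consequence is larger in the Roll-in cohort, because there the trigger defines ITT itself. The subject may lose cohort membership and also the follow-up during which later major bleeding or death would be collected.

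**Working it through.** The protocol states no figure on this point, so the main check is to apply its rules to one case: venous access, transseptal puncture, perforation with tamponade, and the procedure stopped before the LAAO sheath enters.

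**Randomized subject**
- Sections 8.8.3 and 8.8.6: in ITT from randomization, and cannot later become a Screen Failure. The event counts in the primary safety analysis.
- Section 8.8.4: no sheath entry, so not Attempted. The event is absent from the supportive primary analysis and from any secondary analysis run in that set.
- Section 14.6: adverse events are tabulated in ITT Randomized as well as Attempted and Implanted, as applicable, so the event can still appear in the ITT table.

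**Roll-in subject**
- Section 8.8.1: no sheath entry, so never in Roll-In ITT.
- Section 8.6.2.2.2, criterion 4: an effusion above 10 mm, or tamponade physiology, is an exclusion. Appendix A defines a Screen Failure as a consented subject who at any point fails to fulfil all eligibility criteria. On that reading the 45-day rule of 8.8.1 applies.
- If the complication is not an exclusion (a vascular injury, for example), 8.8.1 gives the subject no class at all.
- Section 9.5.7 lets a non-randomized subject found ineligible on ultrasound before the delivery system is introduced leave with no further follow-up. It may be meant only for baseline imaging, but it does not say so.
- Section 12: adverse events are collected from consent, so the event itself is recorded.

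**Same case, but the sheath enters later.** The subject is Attempted (or Roll-In ITT), and nothing in the text removes the earlier event. Only abandoned cases are affected.

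**Size.** The protocol gives no rate of complications before sheath entry, nor of how often they end the case. Let q be the share of subjects with an endpoint complication and no sheath entry, assumed to lie between 0.1% and 1.0%. Inputs from the protocol: at most 300 roll-ins; up to 1600 randomized 1:1, so 1600 / 2 = 800 per arm; a 15% safety event rate (section 14.1.2).

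| Assumed q | Roll-ins, 300 × q | Per arm, 800 × q | Attempted rate, (0.15 − q) / (1 − q) |
|---|---|---|---|
| 0.1% | 0.3 | 0.8 | 0.149 / 0.999 = 14.9% |
| 0.25% | 0.75 | 2 | 0.1475 / 0.9975 = 14.8% |
| 0.5% | 1.5 | 4 | 0.145 / 0.995 = 14.6% |
| 1.0% | 3 | 8 | 0.140 / 0.990 = 14.1% |

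**Primary safety test.** The stated sample size reproduces. With 15% in both arms, a 5.8% margin, one-sided 0.025 and 80% power, n per arm = (1.960 + 0.842)² × 2 × 0.15 × 0.85 / 0.058² = 595, or 1190 in total against the stated approximately 1200. Nothing in that calculation uses the Attempted definition.

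**The case against.** The strongest reply is that starting an attempt when the LAAO system enters the body is a coherent definition of device exposure, used alike in 8.8.1, 8.8.4 and Appendix A. The window before it is also short. Sections 7.4.1 and 7.4.1.3 describe the Access Sheath as the route from the femoral vein across the septum, so injuries caused by that sheath fall after the trigger.

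A reader might infer more than the text supports:
- *That all access and puncture complications drop out.* They do not. The rules classify subjects, not events, and only cases abandoned before sheath entry are affected.
- *That the primary safety result or the comparison of arms is biased.* Primary safety uses ITT Randomized, and the trigger is the same in both arms.
- *That roll-in events vanish from the safety summary.* They are collected from consent, and the summary in section 8.2.1 is not expressly limited to Roll-In ITT.
- *That the learning-curve comparison is biased.* Section 8.2.1 names CLAAS subjects from the RCT without naming a population. Against the Attempted set the trigger matches; a mismatch arises only if RCT ITT is the comparator.
- *That Screen Failure status is certain.* Section 8.8.1 does not say that a complication of the procedure is a loss of eligibility; the text permits that reading without stating it.

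All of this stands and limits the point. It does not answer the remaining problem. Collection from consent helps only while follow-up lasts, and a subject released at 45 days contributes no later bleeding or death to a 12-month endpoint. Nor is the trigger uniform across the study: section 8.8.2 uses introduction of the Delivery Catheter for the conscious sedation cohort, whose safety is to be compared with the CLAAS arm of the RCT.

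**Conclusion.** The point holds in a limited form. As written, an early complication that ends the case before sheath entry excludes a randomized subject from the Attempted set. It keeps a roll-in subject out of Roll-In ITT and, if the complication is read as loss of eligibility, shortens follow-up from 18 months to 45 days.

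The number affected cannot be derived from the protocol and is probably a handful. The range of 0.3 to 3 roll-ins and 0.8 to 8 subjects per arm rests wholly on the assumed 0.1% to 1.0%. Even at the top of that range, a 15% event rate would read 14.1% in the Attempted set. This is an inexpensive improvement to the description of procedural safety and does not threaten the primary conclusion.

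**What to change.** - In sections 8.8.1 and 8.8.4 and in the Appendix A entries for the Attempted and Intended populations, define an attempt as the start of the invasive LAAO procedure: first venous puncture, or introduction of any sheath or transseptal system.
- State that a roll-in subject past that point cannot become a Screen Failure, counts in the Roll-in safety set, and is followed like other attempted subjects without an implant.
- Reconcile the later trigger in section 8.8.2 with this definition.
- Reconcile the exit wording in section 9.5.7, stating whether it covers only baseline imaging before any invasive step. That section also calls some randomized subjects Screen Failures with 45 days of follow-up, contrary to 8.8.3 and 8.8.6. That conflict is separate from the attempt rule but should be settled in the same edit.

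The cost is wording in a few places, telehealth follow-up for a few more roll-in subjects, and possibly slightly higher reported complication rates. The primary analysis and the sample size do not change.

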8.4 Estimated Enrollment Time

The trial is anticipated to take approximately 8 years, depending on the rate of enrollment. Enrollment is expected to take approximately 3 years, and each subject will be followed for a total of 5 years. Follow-up visits may occur as part of an expanded access and/or post-approval study, should the CLAAS System gain approval for commercial distribution prior to the subject's 5-year visit.

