8.8.5 Implanted Population

The Implanted Population includes all subjects in the Attempted Population who undergo the study procedure and receive a LAAO device. Please note that this includes subjects who have received the assigned device or an alternative commercially available device. For subjects assigned to the CLAAS Cohort, the assigned device is the CLAAS Device. For subjects assigned to the Control Cohort, the assigned device will be the first device introduced into the body.

If at any point, a patient was implanted with a LAAO device and has that implant removed, the patient must be followed through the Primary Safety and Efficacy Endpoints with telehealth/phone call visits (at all visits including 7-days, 45-days, 6-months, 12-months, and 18-months) assessing only: QVSFS, AE Assessment, and Concomitant Medication Assessment. These subjects will not be required to have subsequent protocol mandated imaging and will not be required to follow the medication requirements.

These subjects are followed in accordance with the follow-up schedule.

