9.12 Eighteen-month Follow-up ± 30 Days (Clinic Visit)

All subjects will complete a clinical assessment at 18 months (± 30 days) post-procedure with an in-person clinical visit to complete the Primary Endpoint Assessment. The 18-month follow-up visit will include the following assessments:

- Neurological assessment may be performed by a non-delegated neurology professional (e.g., board-certified or board-eligible neurologist, neurology fellow, neurology physician assistant, or neurology nurse practitioner, or NIHSS- and/or mRS-certified staff where applicable), as long as assessments are completed as part of standard of care and documentation of current certification is maintained in site Regulatory files.:
 - Questionnaire for Verifying Stroke-Free Status (QVSFS) If any question is answered "Yes," a formal neurologic examination and evaluation must be performed by a board-certified neurologist or clinical designee (e.g., neurology fellow).
 - NIH Stroke Scale (NIHSS).
 - Modified Rankin Scale (mRS) to establish the disability or dependence in the daily activities of people who have suffered a stroke or other causes of neurological disability at baseline.
- Current concomitant medications documentation.
- Adverse event assessment.

Prior to concluding the visit, research staff should also review the follow-up requirements with the subject to help ensure continued study compliance.

NOTE: Subjects who had a procedure attempt but did not receive an implant must be followed through the Primary Endpoints with a minimum of telehealth/phone call visits at all visits including 7-days, 45-days, 6-months, 12-months, and 18-months (imaging not required and protocol mandated medication therapy not required). After the 18-Month follow-up, these subjects will have completed all required study assessments.

9.13 Annual Follow-up 2 – 5 Years ± 60 Days Post Index Procedure (Telehealth)

All subjects will complete annual telehealth visits (at a minimum) at 2, 3, 4 and 5-years (± 60 days) post-index procedure to include the following assessments:

- Questionnaire for Verifying Stroke Free Status (QVSFS) If any question is answered "Yes," a formal neurologic examination and evaluation must be performed by a board-certified neurologist or clinical designee (e.g., neurology fellow).
- Current concomitant medications documentation.
- Adverse event assessment.

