- In the event of a Stroke, 90 days following the event, documentation of a Neurologic evaluation including Modified Rankin Scale (mRS) is required. The Sponsor may request records (including imaging) related to this evaluation.
- In the event of a Systemic Embolism, 90 days following the event, documentation of a clinical evaluation is required. The Sponsor may request records (including imaging) related to this evaluation.

10 Study Completion

Subject participation in the study ends after the 5-year follow-up assessment, and the study completion form should be submitted at this time.

11 Protocol Deviations

All deviations from the requirements of this Clinical Investigation Plan will be considered protocol deviations. For any protocol deviation, a Protocol Deviation form should be completed in the eCRF indicating the type and reason for the deviation in accordance with FDA requirements outlined CFR 812.140 (a) (4), ISO 14155:2020, and other applicable regulations.

Protocol deviations include but are not limited to:

- Failure to obtain informed consent, or failure to obtain informed consent prior to the performance of study-specific procedures or assessments.
- Enrollment of a subject who did not meet all study inclusion criteria, or who met one or more study exclusion criteria.
- Failure to complete protocol-specified assessments, or completion of protocol-specified assessments outside of the protocol-defined time frame.

The Investigator shall not deviate from the protocol, however if a deviation from the protocol is deemed necessary by the Investigator to protect the safety or physical well-being of a subject, the Investigator is requested to notify the Sponsor as soon as possible (if possible, before the deviation has occurred) and IRB/REB/EC, if required.

The use of waivers in this clinical study protocol is prohibited unless approval is received in writing from the Sponsor or designee.

The Sponsor or its representatives will evaluate deviations to the clinical investigation plan during monitoring visits. Individual event corrective actions may be recommended at that time. In addition, deviations occurring across all investigational sites will be reviewed by the Sponsor or its representative on a periodic basis to determine if more global preventative actions may be required. The Sponsor may terminate an investigator or site's participation in the study (see Section 18.1.7).

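### Randomised subjects who receive no implant get a lighter 18-month assessment and finish at 18 months, so observation within the ITT set depends on a post-randomisation outcome

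*Protocol*

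**What the plan says.** **General rules.** Section 8.4 says "each subject will be followed for a total of 5 years", and section 10 says "Subject participation in the study ends after the 5-year follow-up assessment". Section 9.13 adds: "All subjects will complete annual telehealth visits (at a minimum) at 2, 3, 4 and 5-years". Section 9.12 brings all subjects in at 18 months "with an in-person clinical visit to complete the Primary Endpoint Assessment", with QVSFS, NIHSS and mRS.

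**Rules for randomised subjects without an implant.** Section 8.8.3 (group 2: found ineligible after randomisation and before the procedure) and section 8.8.4 (attempted, no device placed) set telehealth or phone contact "assessing only: QVSFS, AE Assessment, and Concomitant Medication Assessment". Both then close with: "After the 18-Month visit, these subjects will have completed all required study assessments". The note in 9.12 repeats the exception for attempted subjects, but there telehealth is a minimum. Under 14.2 the ITT Randomized population is the one used for both primary endpoints, so these subjects are in it.

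**Explanted subjects.** Section 8.8.5 begins "If at any point, a patient was implanted with a LAAO device and has that implant removed" and applies the same reduced set, with visits named only up to 18 months. It has no completion sentence. It ends by saying that these subjects follow the follow-up schedule, without making clear whether that means explanted subjects or the whole Implanted Population.

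**A third rule.** Section 9.5.7 calls a randomised subject who fails eligibility on procedural ultrasound a Screen Failure and follows that subject for 45 days. The note in 9.9 also stops at 45 days. Section 8.8.3 requires 18 months for such subjects, and 8.8.6 says an ITT subject can no longer be a Screen Failure.

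**The concern.** Whether a device ends up in place is a result of the assigned treatment. In an unblinded comparison of different devices it can differ by arm. If that result decides how, and for how long, an ITT subject is observed, ascertainment is no longer the same in both arms by design.

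Two things are at stake. First, the 18-month effectiveness comparison: a missed stroke or embolism among non-implanted subjects lowers the event rate of the arm with more of them, and if that is the CLAAS arm the error runs toward non-inferiority. Second, any long-term summary: a selected group, left without appendage closure and so probably at above-average stroke risk, drops out at 18 months while everyone else is followed to 5 years.

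**Working it through.** **1. The plan's own power figure.** Inputs from 14.1.1: event rate 4.14%, margin 3.2%, one-sided alpha 0.025, 1600 subjects 1:1, 10% attrition, so 1600 × 0.9 / 2 = 720 per arm. SE = √(2 × 0.0414 × 0.9586 / 720) = 0.0105. Power = Φ(0.032 / 0.0105 − 1.96) = 86.2%, in line with the stated figure of more than 85%. Nothing below changes sample size or power.

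**2. How many subjects.** Section 6.4 reports implant failure in 4/22 (phase 1) and 1/42 (phase 2).
- Phase 2 alone: 1/42 = 2.4%; 800 × 1/42 ≈ 19 CLAAS subjects.
- Pooled: 5/64 = 7.8%; 800 × 5/64 ≈ 62. All four phase 1 failures came before the Large device was available, so this is an upper end.

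The protocol gives no rate for 8.8.3 group 2, who would add to these counts.

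**3. Expected events in them.** Section 6.2 puts untreated stroke risk at about 6% per year. Assuming a constant hazard and no treatment:
- 0 to 18 months: 1 − exp(−0.09) = 8.6%, or 1.6 to 5.4 events, against 800 × 0.0414 ≈ 33 expected in the arm.
- 18 months to 5 years: exp(−0.09) − exp(−0.30) = 17.3%, or 3.3 to 10.8 events (0.41 to 1.35 percentage points of 800).

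If these subjects are anticoagulated and the roughly 60% reduction in 6.2 applies, the hazard is 2.4% per year. The 19 subjects then give 19 × (1 − exp(−0.036)) ≈ 0.7 events by 18 months and 19 × (exp(−0.036) − exp(−0.12)) ≈ 1.5 afterwards.

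**4. Effect on the 18-month test.** The excess of non-implanted subjects in the CLAAS arm and the share of their events missed are both assumptions. With an event rate of 9% (6% × 1.5 years), bias = excess × 0.09 × share missed. At the margin, SE = √(0.0734 × 0.9266 / 720 + 0.0414 × 0.9586 / 720) = 0.0122, and type I error = Φ(bias / SE − 1.96).

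| Excess | 10% missed | 25% missed | 50% missed |
|---|---|---|---|
| 2% | 0.02 pp; 2.6% | 0.05 pp; 2.7% | 0.09 pp; 3.0% |
| 5% | 0.05 pp; 2.7% | 0.11 pp; 3.1% | 0.23 pp; 3.8% |
| 8% | 0.07 pp; 2.9% | 0.18 pp; 3.5% | 0.36 pp; 4.8% |

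Each cell gives the bias in percentage points, then the one-sided type I error.

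**5. Visit window against analysis time.** The schedule in section 5 sets the 18-month visit at day 545 ± 30; 14.5.1 estimates the endpoint at day 547. A non-implanted subject seen at day 515 is finished 547 − 515 = 32 days early, and one seen on target is 2 days short. An implanted subject seen on the same day remains under follow-up. At 6% per year, 32 days carries 0.06 × 32/365 ≈ 0.5% risk per affected subject, about 0.1 event across 19 subjects.

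**The case against.** The strongest reply is that the exception is deliberate: it is written in 8.8.3 and 8.8.4 and repeated in 9.12, and 8.11 allows completion to vary by cohort. Contact runs through both primary endpoints (12 and 18 months), the formally tested secondary endpoints are at 45 days, and the protocol names no hypothesis test in years 2 to 5. Backstops exist: a positive QVSFS requires a formal neurologic examination, and a suspected stroke or embolism brings the subject in under 9.14. Between discharge and month 12, implanted subjects' scheduled stroke screen is also the telehealth QVSFS, so the scheduled difference comes down to one visit. The counts also run high: anatomy must now suit both devices, a subject given an alternative commercial device counts as implanted, and control-arm failures offset the excess.

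Most of this stands, and it limits the size. It does not remove the point. The backstops rely on self-report or suspicion, which a scheduled NIHSS/mRS does not. The 9.12 note calls telehealth a minimum while 8.8.4 restricts what is assessed, so sites may differ. The general 5-year statements make no allowance for the exception.

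A reader might infer two stronger things. One is that explanted subjects are released at 18 months. Section 8.8.5 does not say so; 9.13 covers all subjects, and 12.3 continues collecting serious events, device deficiencies and events of special interest after month 18. The other is that an arm with more failed implants would look better than one with fewer. These subjects stay in the ITT analysis at about 8.6% risk against 4.14%, so more than 1 − 4.14/8.6 = 52% of their events would have to be missed. With the backstops in place, the documents do not support that.

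**Conclusion.** The point holds for randomised subjects who receive no implant: their assessment and length of follow-up differ from the rules stated for all subjects, on the basis of a post-randomisation outcome. For the 18-month test the expected effect is a small under-count in the arm with more non-implants. Type I error is about 3.1% in a middle case and 2.6% to 4.8% across the range; these rest on assumed excess and miss rates and are not predictions. The visit window adds a very small further loss.

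The clearer cost is in years 2 to 5: about 3 uncollected events at a 2.4% failure rate and untreated 6% per year, about 1.5 if anticoagulated as assumed above, and up to about 11 at the pooled 7.8%.

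For explanted subjects the finding is ambiguity only: after an explant at, say, month 20, every visit that 8.8.5 names has passed, and the text does not settle what remains scheduled. The 45-day rule is a direct contradiction and, if followed, would cut short primary-endpoint follow-up in ITT subjects. Overall this is an inexpensive improvement and does not threaten the design.

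**What to change.** - In 8.8.3, 8.8.4 and the 9.12 note, apply the existing 18-month in-person NIHSS/mRS visit to every randomised subject, with telehealth only if the subject cannot attend. Replace completion at 18 months with the annual telehealth calls of 9.13 to 5 years.
- Require endpoint status to be ascertained through day 547 when the 18-month visit falls earlier.
- In 8.8.5, state that a subject explanted at any time stays on the remaining telehealth schedule to 5 years, and make clear whom the closing sentence covers.
- In the same edit, reconcile the 45-day and Screen Failure wording for randomised subjects in 9.5.7 and 9.9 with 8.8.3 and 8.8.6.

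No imaging or medication requirement is added, and sample size and power are unchanged. The cost is one clinic visit and four calls, all already in the schedule, for each subject in a small share of the trial (roughly 2% to 8% of an arm on the figures above), plus some site work and consent wording.
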